12.2.3.2. Secondary Endpoints

The incidence of AEs, SAEs, laboratory parameters and vital signs will be summarized descriptively by treatment group and study visit. The AEs will be summarized at $\geq 1\%$ (common) and $\geq 10\%$ (very common) level.

For the secondary safety endpoints, the proportion of participants with an abnormal change or new abnormal change will be compared by a Fisher's exact test between tafenoquine and placebo. The 95% CI of the abnormality rate will be summarized by Clopper Pearson Exact methodology. A logistic regression will be used to compare the risk of having the abnormality (odds ratio and 95% CI) between tafenoquine and placebo. These analysis methods will be applied to the following secondary safety endpoints: proportion of participants with abnormal changes from baseline observed on qFAF, proportion of participants with corneal deposits from slit lamp examination of the corneal epithelium, proportion of participants with new abnormal changes from baseline observed with color retinal digital photography (conventional and wide field), proportion of participants with new abnormal changes from baseline observed with microperimetry, proportion of participants with any new anomaly on the backlit ETDRS chart, proportion of participants with any clinically significant change in ETDRS BCVA (defined as ≥ 15 letter change [≥ 3 lines] of change in ETDRS BCVA at 4 meters), proportion of participants who develop a new color deficiency using the FM-100 hue test, proportion of participants who develop a loss of 0.12 or greater logCS on the Mars letter contrast sensitivity test, proportion of participants who develop a new identified psychiatric disorder, and proportion of participants with an AE of dizziness or vertigo and severity as assessed by the DHI.

For time to event safety endpoint, a log-rank test will be used to compare the time to onset/resolution of the event between tafenoquine and placebo. Cox regression will be used to compare the risk of having the safety endpoint (hazard ratio and 95% CI) between tafenoquine and placebo. The survival analysis methods will be applied to the endpoints of time to onset, and time to resolution of corneal deposits after treatment cessation.

Change from baseline in BCVA, key SD-OCT continuous parameters, and LSEQ component scores will be analyzed by a random intercept mixed model to account for correlation between repeated measures. Treatment effect (difference and 95% CI) on the change from baseline variables will be estimated across study visits.

Specifically, the following assessments will be conducted for secondary safety endpoints, and the extra analyses, if mentioned as below, will be applied.

- Mean change from baseline in key SD-OCT parameters including CST, TMV volume, and parafoveal (inner ring of ETDRS grid) retinal thickness and the proportion of participants with ellipsoid or interdigitating zone disruption. The difference in the proportion of participants with clinically significant ophthalmologic changes (as defined in the primary endpoint) between treatment group and the placebo group will be calculated. In addition, the change from baseline in individual SD-OCT and qFAF parameters listed in [Appendix 1](#) and [Appendix 2](#) will be tabulated and compared between tafenoquine and placebo-treated groups.
- Proportion of participants with abnormal changes from baseline observed on qFAF using the Spectralis HRA+OCT device with grey scale values extracted from these images for statistical analysis using qFAF software (Heidelberg Engineering).
- Mean change from baseline in BCVA. Changes from baseline in BCVA results by the ETDRS chart will be tabulated and compared between the two groups. A clinically significant deterioration is defined as a reduction of more than 4 letters from baseline (Week 1, Day 1 [Visit 2]) of 0.08 logMAR. The M-chart will be used to quantify the severity of the distortion (if detected). An additional analysis of BCVA changes will include the proportion of participants experiencing a 1-4 letter change (less than one line of ETDRS visual acuity change), a 5-9 letter change (1 line, but less than 2-line change), 10-14 letter change (2 lines, less than 3 lines) or 15 or more letter change (3 lines or more) in BCVA from baseline. A ≥ 15 letter (≥ 3 line) or more change in ETDRS BCVA at 4 meters is considered clinically significant.
- Proportion of participants with corneal deposits from slit lamp examination of the corneal epithelium. Severity of corneal deposits by impairment of vision: The proportion of participants with grades I to IV keratopathy (Orlando grading system for cornea Verticillata, a specific pattern of corneal deposits. For participants with corneal deposits identified from slit lamp examination, the time to first onset and time to resolution after treatment cessation will be tabulated. Corneal structural changes are defined as changes from Baseline (Week 1, Day 1 [Visit 2]) of two or more grades of corneal changes. These data will also be provided in a listing.
- Time to onset of corneal deposits and overall time duration to resolution post treatment start.
- Time duration to resolution of corneal deposits after treatment cessation.

- Proportion of participants with new abnormalities compared with baseline observed with color retinal digital photography (conventional and wide field);
- Proportion of participants with new abnormalities compared with baseline observed with microperimetry;
- Proportion of participants with any new anomaly on the backlit ETDRS chart;
- Proportion of participants who develop a new color deficiency using FM-100 hue test;
- Proportion of participants who develop a loss of 0.12 or greater logCS on the Mars letter contrast sensitivity test;
- Retinal changes (structural) and the impact on macular function (functional) will be tabulated for each time point for each eye. The macular function tests include BCVA (ETDRS), Color vision assessment with FM-100 hue test, M-chart, and microperimetry. Clinically significant changes in any of the five tests are will be counted as having an impact on macular function. Retinal abnormalities on funduscopy, digital fundus photography (conventional and wide field), SD-OCT and qFAF at Screening are considered to be structural changes but may not affect macular function with 12 months of treatment with tafenoquine.
- The proportion of participants with retinal abnormalities identified from digital photographs will be tabulated for each time point and overall. These data will also be provided in a listing;
- Proportion of participants who develop a new, current psychiatric disorder in accordance with the DSM-5 as assessed with the M.I.N.I 7.0.2 assessment questionnaire and suicidal ideation or suicide attempt by C-SSRS interview;
- Proportion of participants with a TEAE of dizziness or vertigo and severity as assessed by the DHI; and
- Mean change from baseline in GTS, QOS, AFS, and BFW as assessed by the LSEQ.

Grading of tafenoquine induced corneal deposits (cornea Verticillata):

The severity of cornea Verticillata (vortex pattern of benign corneal deposit) detected on slit-lamp microscopy will be classified according to the grading system for amiodarone-induced cornea Verticillata proposed by [Orlando 1984](#). Amiodarone and hydroxychloroquine are both cationic amphiphilic drugs which induces phospholipidosis in the form of corneal deposits similar to tafenoquine.

Grade I: punctate opacities that coalesce to form a horizontal line in the inferior third of the cornea. This earliest sign is characterized by golden-brown micro deposits in the epithelium just anterior to the Bowman's membrane. These appear as a "dusting" of the cornea at the inferior pupillary margin in the mid periphery. There is no fluorescein epithelial punctate staining, foreign body sensation or other ocular symptoms.

Grade II: additional branching or arborization, resembling cat's whiskers. In this stage, the deposits become aligned in a more linear pattern and extend from the inferior pupillary margin towards the limbus. This give the appearance much like that of a "cat's whisker. There is a clear zone between the margin of the deposits and the limbus.

Grade III: the branches increase to assume a verticillate or whorl-like pattern. Linear "filament-like" deposits seen in grade II Verticillata increase in number and extend as

branches from the inferior pupillary area into the visual axis. A whorled pattern is seen in the pupillary axis of the cornea.

Grade IV: irregular clumps of pigment accompanying the whorled opacities. From grade III Verticillata, irregularly round “clumps” of golden-brown deposits can develop defining grade IV verticilla.

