Ocular tissue imaging by means of OCT has become essential for the evaluation of retinal diseases and treatment decisions ([Wenner 2011](#)). SD-OCT, also known as Fourier-domain OCT has resulted in improved resolution of the B-scan images ([Grover 2009](#)). These newer high-resolution instruments can show localized thinning of the retinal layers in the parafoveal region and confirm drug toxicity. Loss of the inner/outer segment line (now known as the ellipsoid zone) may be an early objective sign of parafoveal damage ([Marmor 2016](#)). Normal reference values for macular thickness have been previously established by Time Domain (TD) Stratus OCT and this study will use a normative range value of 222-318 μm for study participants ([Appendix 4](#)) using SD-OCT. TD-OCT is no longer recommended ([Section 2.1.1.3](#)). A literature search showed that macular thickness can be different between different racial or ethnic groups and can be further affected by age, gender, refractive error and axial length. It is important to note that changes in foveal thickness are expected to be found in eyes with symptomatic macular pathology ([Wenner 2011](#)). However, toxic maculopathy tends to start in the parafoveal region without acuity loss. Therefore, total macular volume and parafoveal (inner ring of ETDRS grid) thickness are also examined as one of the secondary endpoints in this study.

Table 1: Summary of Ophthalmologic AEs: Tafenoquine Recommended Regimen Group vs Placebo and Mefloquine

	Number (%) of Subjects		
	Tafenoquine 200 mg daily x 3 days, then 200 mg weekly (Recommended Regimen) (n=825)	Placebo (n=396)	Mefloquine 250 mg daily x 3 days, then 250 mg weekly (n=309)
Included Studies	030, 033, 043, 045, 057	030, 043, 044, 045, 057	030, 033, 045
AEs leading to Discontinuation			
Metamorphopsia	0	1 (0.3%)	0
Night blindness	1 (0.1%)	0	0
Visual acuity reduced	1 (0.1%)	0	0
Ophthalmologic SAEs			
Keratopathy	5 (0.6%)	0	0
Retinal disorder	2 (0.2%)	0	1 (0.3%)
Metamorphopsia	0	1 (0.3%)	0

Table 1: Summary of Ophthalmologic AEs: Tafenoquine Recommended Regimen Group vs Placebo and Mefloquine (Continued)

	Number (%) of Subjects		
	Tafenoquine 200 mg daily x 3 days, then 200 mg weekly (Recommended Regimen) (n=825)	Placebo (n=396)	Mefloquine 250 mg daily x 3 days, then 250 mg weekly (n=309)
Ophthalmologic AEs Occurring in ≥1% of Study Subjects			
Conjunctivitis	24 (2.9%)	18 (4.5%)	13 (4.2%)
Keratopathy	68 (8.2%) ^a	0	0

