9.2.6. Ophthalmic Assessments

The ophthalmic assessments will be conducted at Screening at (Visit 1b or 1a depending on site and subject preference) and repeated at Weeks 12, 24, and 52 of the Treatment Phase and at the EOS visit (Week 64). Ophthalmic assessments will be repeated at Week 76 (Visit 8) and quarterly thereafter to 12 months if ongoing or new ophthalmic abnormalities are identified at the Week 64 visit. Microperimetry testing will be conducted at Screening twice with the first result discarded to minimize learning effect and at Weeks 24, 52 and 64. Non-clinically significant abnormalities at Baseline (Week 1, Day 1) will be recorded as medical history and will only be followed up after Week 64 if the abnormality worsens during the Treatment Period.

Please note, only tests that are abnormal at the Week 64 visit will be followed up in Weeks 76, 89 or 104 (Visits 8, 9, or 10). For example, if corneal deposit was the only abnormality found during Week 64, then there is no need to repeat any of the ocular examinations except for corneal photography and corneal slit lamp examination at Weeks 76, 89 or 104. Therefore, not all ophthalmic testing will need to be completed in Phase 3 of the study at the discretion of the PI.

Specific test parameters will be provided in the ophthalmology manual for the study.

Routine ophthalmic tests will include the following:

- BCVA (ETDRS);
- Color vision assessment with FM-100 hue test. The Lanthony D15 test will be administered immediately prior to the FM-100 test to reduce learning affects.
- Mars letter contrast sensitivity test;
- M-chart;
- Slit lamp examination of anterior and posterior segment
- Intraocular pressure measurement
- Microperimetry (Weeks 24, 52 and 64).

- SD-OCT (including wide field macula scan);
- qFAF (set of 3 images to ensure consistency in measurement);
- Digital photograph of corneal surface (conventional and wide field); and,
- Digital photograph of retina (conventional and wide field)

Abnormal results may be further investigated using microperimetry, FM-100 hue test, Mars contrast sensitivity letter reading test, M-chart, slit lamp examination, SD-OCT (including wide field macula scan) and qFAF depending on the nature of the abnormality.

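### Mars contrast sensitivity, FM-100 hue and microperimetry are analysed only as yes/no outcomes; adding a change-from-baseline analysis would recover substantial power for a small general loss

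*Combined protocol and SAP*

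**What the plan says.** Section 12.2.3.2 (Secondary Endpoints) lists the three tests among the binary outcomes:

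- Mars: "proportion of participants who develop a loss of 0.12 or greater logCS on the Mars letter contrast sensitivity test".
- Microperimetry: "proportion of participants with new abnormal changes from baseline observed with microperimetry".
- FM-100: "proportion of participants who develop a new color deficiency using the FM-100 hue test".

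Each proportion "will be compared by a Fisher's exact test between tafenoquine and placebo". Clopper-Pearson intervals are given for the rates, and "A logistic regression will be used to compare the risk of having the abnormality", with an odds ratio and 95% CI.

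The same section then sets out the full-scale analysis: "Change from baseline in BCVA, key SD-OCT continuous parameters, and LSEQ component scores will be analyzed by a random intercept mixed model". Mars, FM-100 and microperimetry are not on that list. The Statistical analysis part of the Synopsis makes the same split. A further item in 12.2.3.2 tabulates structural and functional changes by visit and eye; it too counts clinically significant changes, and its named tests do not include Mars.

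Section 2.1.1 notes that "toxic maculopathy tends to start in the parafoveal region without acuity loss". Section 9.2.6 shows that the tests are repeated after baseline; for example, "Microperimetry testing will be conducted at Screening twice with the first result discarded to minimize learning effect and at Weeks 24, 52 and 64".

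**The concern.** Acuity is the only visual function test that the plan compares on its full scale, and Section 2.1.1 describes early maculopathy as sparing acuity. The other function tests are reduced to whether a participant crossed a line. With about 300 per arm, a mean difference in contrast sensitivity could be estimated closely. A threshold count uses only part of that information, and logistic regression does not recover it because its outcome is the same yes/no variable.

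At stake is how far a null result can be read. A non-significant comparison of proportions, even with its interval, bounds the difference in rates of a 0.12 logCS loss. It does not bound the average loss. A between-arm mean difference with a 95% CI would.

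**Working it through.** **1. The plan's own figures.** Section 12.1 assumes a 1% event rate in both arms, a 2.5-point margin, 300 per arm and one-sided 2.5%.

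- Power = Φ(0.025 / √(2 × 0.01 × 0.99 / 300) − 1.96) = 0.868; the plan states 86%.
- Chance of at least one event in 300 at 1% = 1 − 0.99^300 = 0.951; the plan states 95%.

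Both reproduce, but they concern the primary endpoint. No power is stated for Mars, FM-100 or microperimetry.

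**2. Inputs for Mars.** From the documents: 300 per arm (Section 5.6), two-sided 5% (Section 12.1), cut at 0.12 logCS (Section 12.2.3.2). Assumed, because the documents give neither: SD of change σ from 0.06 to 0.15 logCS, and a mean loss of 0.02 logCS on tafenoquine. Change is taken as normal, with one value per participant.

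**3. A small general loss.**

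- Mean change: two-sample t-test, noncentrality (0.02/σ) × √(300/2).
- Cut: p0 = 1 − Φ(0.12/σ) on placebo, p1 = 1 − Φ((0.12 − 0.02)/σ) on tafenoquine, with power from exact enumeration of the two-sided Fisher test.

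| σ | 0.02/σ | p0 | p1 | Power, mean | Power, Fisher |
|---|---|---|---|---|---|
| 0.06 | 0.333 | 2.3% | 4.8% | 98% | 31% |
| 0.08 | 0.250 | 6.7% | 10.6% | 86% | 34% |
| 0.10 | 0.200 | 11.5% | 15.9% | 69% | 30% |
| 0.12 | 0.167 | 15.9% | 20.2% | 53% | 25% |
| 0.15 | 0.133 | 21.2% | 25.3% | 37% | 19% |

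With an assumed 20% loss to follow-up (240 per arm) and σ = 0.08, the figures are 78% against 28%.

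**4. Information kept by the cut.** For a small uniform shift the efficiency relative to the mean is φ(z)² / [p(1 − p)], with z = 0.12/σ and p = 1 − Φ(z). At σ = 0.06, z = 2 and this is 0.0540² / (0.0228 × 0.9772) = 0.13. At 0.08, 0.10, 0.12 and 0.15 it is 0.27, 0.37, 0.44 and 0.50. If the loss is instead sized at each σ so that the mean has 90% power, Fisher has 19%, 38%, 51%, 57% and 63%.

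**5. Severe loss in a few.** Suppose a fraction f of the tafenoquine arm loses 0.24 logCS and the rest lose nothing. The mean difference is 0.24f, the tafenoquine variance is σ² + f(1 − f) × 0.24², and p1 = (1 − f)p0 + f × Φ(0.12/σ).

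For f = 5% and σ = 0.06 the mean difference is 0.012, its SE is √[(0.06² + 0.0796²)/300] = 0.00575, and power is Φ(0.012/0.00575 − 1.96) = 55%. On the cut, p0 = 2.3% and p1 = 7.0%, and Fisher has 76%.

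| f | σ | Power, mean | Power, Fisher |
|---|---|---|---|
| 5% | 0.06 | 55% | 76% |
| 5% | 0.08 | 39% | 41% |
| 5% | 0.10 | 28% | 24% |
| 10% | 0.06 | 96% | 99.7% |
| 10% | 0.08 | 87% | 91% |
| 10% | 0.10 | 75% | 71% |

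**6. FM-100 and microperimetry.** The documents give no scale, cut-off, SD or expected rate for either, so no figure can be computed. That either yields an analysable score is an assumption.

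**The case against.** - **The plan already answers acuity-sparing damage.** After its remark on acuity, Section 2.1.1 turns to total macular volume and parafoveal thickness, and Section 12.2.3.2 analyses those SD-OCT measures on their full scale. A reader might infer that the plan has no sensitive analysis for early damage, or that the three function tests were chosen because acuity is spared. The documents support neither. This stands: the gap is in function tests, not in early detection as a whole.
- **The gain depends on the pattern of harm.** A reader might infer that the cut always discards most of the power. It does not. At SD 0.10 to 0.15, with the loss sized for 90% power on the mean, Fisher keeps more than half of that power, and for severe loss in a few it can equal or beat the mean. Section 10.11.1 defines the microperimetry event of special interest as a ring or partial ring; averaging over the field may dilute such a focal defect. This stands, and is why the proportions should stay.
- **A 0.02 logCS mean loss is one-sixth of the plan's threshold** (0.02/0.12), and nothing in the documents calls it a safety concern. Fair; it is an illustrative size. Thresholds are also an accepted form here: Appendix 8 records the FDA asking for BCVA line categories. But BCVA keeps its mean-change analysis alongside them.
- **Detail is deferred.** Section 12 leaves details to a separate SAP whose text is not in the supplied document, so a score analysis there cannot be excluded. The statement here is about Section 12.2.3.2 and the Synopsis, which name the mixed-model outcomes and omit these three.

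**Conclusion.** The point holds as a low-cost improvement; the primary analysis is not affected. The protocol compares Mars, FM-100 and microperimetry between arms only as yes/no outcomes, while BCVA and SD-OCT get both a threshold and a mean-change analysis. For a uniform 0.02 logCS Mars loss, the mean has about two to three times the power of Fisher's test across assumed SDs of 0.06 to 0.15. That rests on assumed SDs, an assumed shift, normality and one value per participant. For concentrated harm the ranking can reverse, so the two analyses are complementary and neither replaces the other. The numerical case is made for Mars alone, the only one of the three for which the documents show a numeric unit.

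**What to change.** In Section 12.2.3.2, the Synopsis and the SAP, before unblinding:

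- Add change from baseline in Mars logCS to the mixed-model outcomes. Add FM-100 and microperimetry scores if they are recorded as scores, transformed or rank-based if skewed.
- State how the two eyes enter the analysis. Section 12.2.3.1 gives an either-eye rule for the primary endpoint only.
- Report the between-arm difference with 95% CI, including at Week 52. The model as written estimates an effect across visits, so this contrast has to be specified.
- Keep the planned proportions, and state what counts as an abnormality on FM-100 and microperimetry.
- Reconcile the Mars threshold: the endpoint includes a loss of exactly 0.12 logCS, whereas the event of special interest in Section 10.11.1 requires more than 0.12.

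No new visits or tests are needed. The cost is some added specification and up to three more unadjusted secondary comparisons, in a plan whose Section 12.2.1 already waives multiplicity adjustment.

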In Study 057, 10 (14.3%) participants in the tafenoquine Recommended Regimen group and 7 (21.9%) participants in the placebo group had evidence of corneal deposits in either eye at screening. After the screening visit, 15 (21.4%) participants receiving tafenoquine and 4 (12.5%) participants receiving placebo developed new-onset corneal deposits in one or both eyes during the study. Approximately 60% of the corneal deposit cases among participants receiving tafenoquine and 100% of the cases among participants receiving placebo emerged by Week 12 of the study. No trends were apparent with respect to the time to onset of these new corneal deposits in participants who did not have corneal abnormalities at screening. New-onset corneal deposits in all four participants in the placebo group resolved within 6 weeks of onset, while in the tafenoquine Recommended Regimen group, corneal deposits resolved within 12 weeks of onset in all but one participant. Corneal deposits in the remaining tafenoquine-treated participant resolved by Week 48.

In summary, benign, reversible corneal deposits have been noted in some participants treated with the tafenoquine Recommended Regimen. Participants are unaware of the development of these corneal deposits; it does not impact vision, and resolves within 1 year in all cases.

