5.6. Route of Administration, Dosage Regimen, Treatment Period, and Justification

The 600 study participants will be randomized to the tafenoquine or the placebo group in a 1:1 ratio using clinical site as a randomization variable; two groups of 300 participants each will be enrolled in each group.

Each active IMP tablet will contain 100 mg tafenoquine. The dose to be administered orally is 200 mg tafenoquine (2 x 100 mg tablets) per day for three consecutive days (loading doses), followed by another 200 mg dose once per week for the following 51 weeks (beginning post-loading dose Day 10). The placebo group will receive identically-matched double-blind placebo tablets. The IMP tablets will be taken with 180 mL of water but there is no restriction on whether the tablets are taken with or without food.

Safety evaluations will include the following assessments: AE evaluation, physical examination, vital signs, laboratory parameters (hematology, biochemistry, and urinalysis). These will be performed at various time points throughout the study to assess baseline function and any changes from baseline after administration of IMP. Hematology, including methemoglobin assessment, biochemistry and urinalysis will be conducted at Screening, Weeks 4, 12, 24, 52, and 64. Clinical laboratory values indicative of an AE at EOS Week 64 will be repeated during the Follow-up Phase at Weeks 76, 89, 104 until resolution or stabilization.

Previous clinical studies support a recommended dosage tafenoquine regimen for malaria prophylaxis of a loading dose of 200 mg once daily for 3 days before travel to a malarious area, followed by weekly 200 mg maintenance doses while in the malarious area, for a period not exceeding 6 months, and an additional dose of 200 mg at one week of return from travel (60P IB).

In this study tafenoquine will be administered for 12 months to confirm the long term safety of tafenoquine past the 6-month safety window for travelers or military personnel who may be in a malarious area for prolonged periods of time.

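### The planned log-rank and Cox comparison of corneal-deposit resolution after treatment cessation is confined to participants who developed deposits, so it is not a randomised comparison

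*Combined protocol and SAP*

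**What the plan says.** Section 12.2.3.2 gives the method for time-to-event safety endpoints: "a log-rank test will be used to compare the time to onset/resolution of the event between tafenoquine and placebo", and "Cox regression will be used to compare the risk of having the safety endpoint (hazard ratio and 95% CI) between tafenoquine and placebo". It then names where these apply: "The survival analysis methods will be applied to the endpoints of time to onset, and time to resolution of corneal deposits after treatment cessation". The statistical analysis part of the synopsis repeats the same two methods. Section 5.2.2 lists time to onset of deposits, and time to their resolution, as secondary endpoints.

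The same section describes who supplies the times: "For participants with corneal deposits identified from slit lamp examination, the time to first onset and time to resolution after treatment cessation" are to be tabulated. No section of the document defines the risk set for the resolution test, says what happens to deposits that clear before the last dose, or labels the between-arm comparison descriptive. Section 12 leaves detail to a SAP whose text is not part of the document.

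Section 2.1.1.1 gives the background from Study 057: "15 (21.4%) participants receiving tafenoquine and 4 (12.5%) participants receiving placebo developed new-onset corneal deposits in one or both eyes during the study". On timing, "100% of the cases among participants receiving placebo emerged by Week 12 of the study", and "New-onset corneal deposits in all four participants in the placebo group resolved within 6 weeks of onset". In the same study, tafenoquine deposits cleared within 12 weeks of onset in all but one participant.

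**The concern.** A log-rank test between randomised arms is a fair test because the arms are alike at time zero apart from treatment. Here time zero is treatment cessation, and entry requires a deposit. Treatment affects who has one: Section 7.7 itself treats these lesions as a sign that a participant is on tafenoquine. The tafenoquine group entering the analysis is largely people in whom the drug produced a deposit. The placebo group is people who formed one for some other reason and for whom stopping treatment withdraws no drug. A hazard ratio between them mixes the cause of the deposit, selection, and any drug effect on clearance.

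The practical risk is misreading. A non-significant result from a handful of placebo cases could be taken to mean that drug deposits clear as placebo deposits do. A significant one could simply reflect two kinds of deposit. Neither describes how fast tafenoquine deposits clear once dosing stops.

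**Working it through.** The plan gives no expected count or power for the resolution analysis; its 86% power belongs to the primary SOSE test. The check therefore starts from the background figures.

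**1. Inputs (Sections 2.1.1.1, 5.6 and 6.2, and Table 1).**
- Allocation: "randomized to the tafenoquine or the placebo group in a 1:1 ratio", 300 per arm.
- Study 057 new onset: 15 on tafenoquine and 4 on placebo. The percentages imply denominators of 70 and 32: 15/70 = 21.4%, 4/32 = 12.5%.
- Study 057 at screening, before dosing: 10/70 = 14.3% and 7/32 = 21.9%, together 17/102 = 16.7%.
- Study 033 subgroup on tafenoquine: 69/74 = 93.2%.
- Table 1 placebo column: no keratopathy in 396. These are adverse-event reports. The table's footnote says keratopathy was reported as an AE only in a Study 033 subgroup, and Study 033 is not among the placebo studies, so this is not a slit-lamp rate.
- Exclusion criterion 3 removes corneal abnormality at Screening.

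**2. Selection.** Scaled to 300 per arm, those ever with a deposit number:
- tafenoquine: 300 × 0.214 = 64 (Study 057) to 300 × 0.932 = 280 (Study 033);
- placebo: 300 × 0.125 = about 38 (Clopper-Pearson limits for 4/32 are 3.5% and 29.0%, so 11 to 87).

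The arms enter the analysis in different proportions and for different reasons. This does not depend on how many placebo cases there are.

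**3. Placebo cases still present at cessation (assumption).** If 12.5% incidence is spread evenly over T weeks and each deposit lasts 6 weeks, the expected number is 300 × 0.125 × 6/T.
- T = 24: 9.4.
- T = 52: 4.3.
- If all onset is by Week 12, as in Study 057: close to 0.
- If instead the pre-dose prevalence recurred: 300 × 17/102 = 50.

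**4. Power of the log-rank test for a hazard ratio of 2.** Assume a two-sided 5% level and that every case resolves. With D total resolutions and placebo share a, power = Φ(√(D·a·(1−a)) × ln 2 − 1.96).
- 3 placebo, 280 tafenoquine: D·a·(1−a) = 3 × 280/283 = 2.97; 1.72 × 0.693 − 1.96 = −0.77; power 22%.
- 9 placebo, 280 tafenoquine: 9 × 280/289 = 8.72; 2.95 × 0.693 − 1.96 = 0.09; power 53%.

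| Placebo cases | 280 tafenoquine cases | 64 tafenoquine cases |
|---|---|---|
| 3 | 22% | 22% |
| 5 | 34% | 32% |
| 9 | 53% | 49% |
| 38 | 98% | 92% |
| 50 | 99% | 96% |

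The placebo count drives the result; the tafenoquine count hardly matters at 3 to 9 placebo cases. The 64 and 280 are participants ever affected, so fewer may still have deposits at cessation.

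**5. What the visits can show.** Slit-lamp examinations fall at Weeks 12, 24, 52 and 64 for everyone (Section 9.2.6). Weeks 52 and 64 are 12 weeks apart, so deposits that last about 6 weeks are poorly timed. After Week 64, only tests abnormal at Week 64 are repeated.

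**The case against.** The case for leaving the plan alone has some force. This is one of many secondary safety analyses, with no multiplicity control and no success criterion, and the primary conclusion does not depend on it. Resolution times are already to be tabulated for participants with deposits. The proportion with deposits is already compared between arms by Fisher's exact test. The SAP could still define the risk set. All of that stands, and it limits the importance of the point. It does not remove it: the test and hazard ratio are committed to in the text without qualification, and the planned Fisher comparison names no time point after cessation, so it does not replace them.

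Three stronger readings are tempting and not supported.
- A reader might infer that there will be almost no placebo data. The documents do not establish that. About 38 of 300 placebo participants could have a deposit at some time on the Study 057 rate, and the inference that few remain at cessation rests on four cases.
- A reader might infer that the claim of full reversibility hangs on this test. Sections 2.1.1.1 and 2.3.2 draw it from completed studies, for example 42 of 69 resolved at 3 months in Study 033 and the rest within 1 year.
- A reader might infer that the onset analysis fails too. It does not, because it can use all randomised participants.

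**Conclusion.** The concern holds for resolution only. The planned p-value and hazard ratio compare two groups selected after randomisation by a finding that treatment affects, and nothing in the document corrects or labels this. That conclusion follows from the design and needs no assumed rate; more placebo cases would improve precision without making the comparison randomised.

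The size of the placebo group is a separate and weaker point. About 0 to 9 of 300 with deposits at cessation is the likely range if Study 057 onset and duration carry over, and up to about 50 if its pre-dose prevalence recurred. Exclusion of corneal abnormality at Screening makes the upper figure less likely. At 3 to 9 cases the test would have about 22% to 53% power for a hazard ratio of 2, so it would probably be uninformative as well as confounded. The change is worth making before unblinding.

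**What to change.** In Section 12.2.3.2, the synopsis and the SAP:

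- Keep the log-rank test and Cox model for time to onset, in all randomised participants.
- Drop the between-arm test and hazard ratio for resolution. Describe time to resolution within the tafenoquine arm, among those with deposits at cessation, by a survival curve with 95% CI. List placebo cases descriptively. State how deposits that clear before the last dose are handled.
- Add a comparison of all randomised participants on deposits present (yes or no) at Week 64, with risk difference and 95% CI. Count those examined and never affected as deposit-free. State how missing Week 64 examinations are handled, and whether an early-termination examination (Section 8.4) counts as Week 64.
- Keep Weeks 76, 89 and 104 descriptive only, because only participants with abnormal Week 64 findings are re-examined then.

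The Week 64 comparison reflects both formation and persistence of deposits, so it complements the within-arm curve and is not itself a measure of reversibility. The cost is wording and one planned secondary p-value. No new visit is needed, since slit-lamp examination at Week 64 is already scheduled for everyone.
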